### 2.- Data análisis

The statistical study will be carried out with the help of the SPSS® version 23.0 software for Windows, using the MATLAB® programming environment for the preparation of the predictive model based on artificial neural networks (ANN).

In the first place, a descriptive analysis will be carried out, both of the sociodemographic and clinical variables, as well as of the analytics and the results of the study.

To describe the quantitative variables that follow a normal distribution, the mean and standard deviation will be used, and the median and interquartile range for those that do not follow a normal distribution, as well as histograms with normality curves for their graphical description.

For the qualitative variables, frequencies and percentages will be used, using bar graphs and/or sectors for the graphic description of those with greater relevance.

A univariate study will be performed to relate the variables studied with the appearance of AF and major postoperative complications. For this, different tests will be used depending on the variable to be studied:

- a) Normal categorical variables: Chi-square test or Fisher's exact test.
- b) Normal continuous variables: Student's t-test.
- c) Non-normal continuous variables: Mann-Whitney U test.

In the results obtained from the univariate study, those variables that show a  $p < 0.1$  after the application of the corresponding tests will be considered as related or candidates to predict AF or major

complications. This value will be considered more conservative, different from the conventionally accepted value of 0.05, with the intention of not ruling out potential variables that could have some influence on the results of the study.

Once the univariate study has been completed, a multivariate study will be carried out, using the logistic regression (RL) method. To do this, a recoding of the variables will be carried out, transforming the categorical variables into dummy variables. It will be verified that the variance inflation factor (VIF) is less than 2 in all cases, thus ruling out important problems of collinearity between the variables.

On the other hand, a predictive model based on artificial neural networks (ANN) will also be developed, using a Multilayer Perceptron, a multilayer neural network of forward connections, without recurrent connections and supervised learning.

In addition, once the model has been designed, an application for mobile devices and/or a web page will be created to prospectively introduce new data on developing cases, in order to obtain predictive information on the possibility of developing AF or a major postoperative complication in each case. in particular, thus being able to help the clinician in decision-making during the postoperative control of these patients.

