## INTRODUCTION

Esophageal cancer is the sixth leading cause of cancer death worldwide, with an incidence that has been increasing in recent years. Surgery is the mainstay of curative therapy for fit patients with the ability to tolerate extensive surgical procedures. Postoperative morbidity associated with esophagectomy is high (around 60%) (1), pulmonary complications occur in 20-50% of patients, and anastomotic leak (AF) has a variable incidence depending on the series (0- 34%) (1, 2) with an associated mortality of 5-36% (3). Regarding gastric cancer, it represents the fifth most common and the second most frequent cause of death from cancer worldwide, with a rate of postoperative complications close to 40-50% (4).

Among the postoperative complications, AF is the most feared, presenting a high mortality rate. This complication is not only associated with a longer hospital stay and increased costs, but also with a worse prognosis of the disease and the patient's quality of life (5). The variability in the rate of AF in the literature is due to the lack of a precise definition that is generally accepted by all groups, as well as the need to establish a reliable and unanimous diagnostic method. In addition to possible technical failures, there are many potential risk factors that may be related to the appearance of this complication. Thus, patients with this type of pathology and due to factors such as accelerated metabolism and decreased intake present a high risk of malnutrition, hypoproteinemia and systemic inflammation, which can alter collagen synthesis, reduce tensile strength in the anastomosis, facilitate poor tissue healing and induce anastomotic dehiscence.

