## OBJECTIVES

Based on the hypothesis of the study, the main and secondary objectives of this study are established:

- Main goal:

\*Design a predictive model based on clinical and analytical variables that allow identifying patients with a high risk of anastomotic leak (main variable) during the postoperative period of esophagogastric surgery.

- Secondary objectives:

\* Design a predictive model based on clinical and analytical variables that allow identifying patients at high risk of other major complications (Clavien-Dindo greater than 3) during the postoperative period of esophagogastric surgery.

\* Individually describe the postoperative evolution of the clinical and analytical parameters studied in patients without major complications or AF and those who did suffer from any of them.

\* Describe the complications and types of AF diagnosed in the study.

\* Assess the day AF was diagnosed and the treatment used for its possible resolution.

\* Assess the day AF was diagnosed and hospital stay.

\* Compare the preoperative Glasgow prognostic score (mGPS) and the biochemical value of inflammatory markers (CRP, Interleukin 6 (IL-6) and procalcitonin) and the appearance of AF.

\* Assess the AF resolution capacity of each technique used.

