### 4.- Sample size

The purpose of the study is to recruit as many patients as possible from all national centers who wish to participate.

For an alpha error of 5% (95% confidence) with a precision of 3% and estimating a number of patients with major complications (including AF) around 30%, the calculation of the sample size yields a total of 847 patients. However, the final sample size may be smaller depending on the proportion of complications detected and the statistical and artificial intelligence models to create the predictive model will be adapted to the event rate provided by the recruited sample.

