## **7.- Follow up**

The patient will be monitored during the first 90 postoperative days, compiling all the specific variables of this study and the possible complications and mortality that occurred in this period.

During the immediate postoperative period, apart from the care applied routinely in each center, patients should be evaluated daily and the clinical and laboratory variables specified later should be collected on days 1, 2, 3, 4 and 6 postoperatively. In the same way, in this postoperative course, the possible complications that appeared during the hospital stay will be compiled.

Subsequently, if the patient is discharged from the hospital, a follow-up will be carried out in the outpatient consultations at 30 and 90 days to evaluate the possible complications that appear in this period and other variables studied will be completed.

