## **8.2.- PARTS of the DATABASE**

After opening the REDCAP application of the AEC, you can access the data set and the different variables to be collected at each moment of the care process and which will be described in more detail below:

The main outcome variable of the study is ANASTOMOTIC LEAKAGE, a categorical variable divided into the following categories, according to the consensus definitions of the Consensus Group on Complications of Esophagectomy (ECCG) (27), which in this study will be applicable both to fistulas occurred after esophagectomy and after gastrectomy:

- NO: If this complication did not occur.
- I: Defect that does not require specific treatment or that can be treated medically or with diet modification
- II: Defect that requires some intervention, but not surgical, such as: drainage by interventional radiology, prosthesis placement, opening of the wound at the bedside, compression or wound healing.
- III: Defect requiring surgical intervention

In relation to this variable, the following data are also included in the study:

- DAY Dx LEAK (DAY of DIAGNOSIS OF THE ANASTOMOTIC LEAK: ordinal variable that shows the number of the postoperative day on which the diagnosis of the anastomotic leak occurred.
- EDA Dx LEAK (LEAK DIAGNOSIS THROUGH ENDOSCOPY): Dichotomous variable: YES/NO.
- CAT Dx LEAK (DIAGNOSIS OF LEAK BY CAT): Dichotomous variable: YES/NO.

The rest of the variables collected in this study are:

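### The leak model has no prediction day and is not limited to patients still undiagnosed, so marker values taken after a leak is found can enter it and its performance may not be that of early warning

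*Combined protocol and SAP*

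**What the plan says.** Section 7 (Follow up) requires that "the clinical and laboratory variables specified later should be collected on days 1, 2, 3, 4 and 6 postoperatively". Section 8.2.2 lists the 20 variables, among them CRP, procalcitonin and IL-6, and adds a preoperative measurement. Neither section makes an exception for a patient whose leak is already diagnosed.

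The main outcome, in section 8.2, is leak graded NO, I, II or III. On its horizon the plan says "The patient will be monitored during the first 90 postoperative days". The day of diagnosis is also recorded, as an "ordinal variable that shows the number of the postoperative day on which the diagnosis of the anastomotic leak occurred". The objectives use that day only descriptively, against treatment and against length of stay ("Assess the day AF was diagnosed and hospital stay").

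In the data analysis section, the first modelling step is: "A univariate study will be performed to relate the variables studied with the appearance of AF and major postoperative complications". Variables with p < 0.1 become candidates. A logistic regression and a multilayer perceptron are then built. The section names no prediction day, no set of patients still at risk, and no cut-off for predictors at diagnosis.

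The same section gives the intended use, an application or web page "to prospectively introduce new data on developing cases, in order to obtain predictive information on the possibility of developing AF". The Hypothesis section likewise gives the aim as earlier diagnosis.

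**The concern.** A prediction model needs a moment at which it is run. At that moment some patients already have a diagnosed leak and need no warning. Values measured later do not yet exist.

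The plan fixes no such moment. A patient whose leak is found on day 3 still has scheduled measurements on days 4 and 6. As the analysis is worded, those values can help select predictors and fit both models, and the patient counts as a leak the model predicted. Yet a marker measured after diagnosis cannot have warned of that leak.

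This concerns the main objective and a tool meant to support bedside decisions. If performance is computed partly on leaks already known, it answers a different question from early warning. If the prediction day is left open until the results are seen, the most favourable day could also be the one reported.

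**Working it through.** **Is there a rule anywhere?** The objectives, follow-up, variable, data-collection, analysis, schedule and limitations sections were read for one. None gives a prediction day, an undiagnosed at-risk set or a cut-off at diagnosis. The day-3 and day-4 cut-offs in the Introduction belong to cited studies, not to this model.

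**How many leaks could be affected?** The plan gives no figure, so this is an illustration.

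Inputs:
- Mean diagnosis day 7 and leak rate 16%: one cited oesophageal series (Introduction). This study also enrols gastrectomies.
- SD of the diagnosis day: not given. Assumed to be 3 to 5 days.
- Shape: assumed gamma or lognormal.
- 847 patients: section 4, used only as a scale. Its stated inputs give 1.96² × 0.30 × 0.70 / 0.03² = 896.4, so 897 rather than 847. Nothing here depends on that difference.

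Formulas, with mean m and SD s: gamma shape (m/s)² and scale s²/m; lognormal σ² = ln(1 + (s/m)²) and μ = ln m − σ²/2. With whole days, before day 4 is P(T ≤ 3.5), before day 6 is P(T ≤ 5.5), and by the end of day 4 or day 6 is P(T ≤ 4.5) or P(T ≤ 6.5).

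Share of leaks diagnosed before the marker day:

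| Mean, SD | Before day 4 (gamma / lognormal) | Before day 6 (gamma / lognormal) |
|---|---|---|
| 7, 3 | 9.7% / 6.9% | 34.6% / 35.1% |
| 7, 5 | 26.8% / 22.4% | 46.8% / 47.8% |

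So the shares are about 7-27% before day 4 and 35-48% before day 6. They move a good deal with the assumptions: the day-6 share is about 2% at mean 9, SD 2, and about 50-60% at mean 6, SD 3 to 5.

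Counts at 847 patients:
- Leaks: 847 × 0.16 = 135.5.
- With a scheduled day-6 measurement after diagnosis: 135.5 × 0.346 = 47 to 135.5 × 0.478 = 65, if every such patient is measured. Deaths, withdrawals and missing values would lower this.

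**What remains under a time-respecting analysis?** At mean 7, SD 3 to 5, with same-day diagnoses excluded:
- After day 4, P(T ≤ 4.5) = 0.192 to 0.371, leaving 135.5 × 0.629 = 85 to 135.5 × 0.808 = 110 leaks.
- After day 6, P(T ≤ 6.5) = 0.489 to 0.581, leaving 135.5 × 0.419 = 57 to 135.5 × 0.511 = 69 leaks.
- Keeping same-day diagnoses at day 6 leaves 135.5 × 0.522 = 71 to 135.5 × 0.654 = 89. The same-day rule moves about 12 to 22 leaks.

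**The case against.** The strongest reply is that competent analysts would restrict by time unprompted, since the day of diagnosis is in the database. They could, but the plan does not commit them to it, and an unstated choice can be made after the results are seen.

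A second reply is that the harm is unproven. This stands. A reader might infer that performance will be overstated, but the documents do not establish that. Effective treatment after diagnosis could bring markers back towards normal and reverse the bias. The Introduction cites one study that found raised markers served diagnosis better than prediction, yet that study also doubted their value for early diagnosis. Another cited study reports a day-4 score that works in patients without symptoms. The plan names no accuracy measure, so any figure for the shift in accuracy would rest on invented inputs.

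Three further readings should not be pressed:
- That leak-treatment variables would become predictors. The objectives limit the model to clinical and laboratory variables, and treatment data exist only for patients with a leak. Pathological stage, listed under general data, is the fairer example of something that may be unknown on the prediction day.
- That a model using day-6 values is faulty because it runs only from day 6. That is equally true of a sound model set at day 6.
- That no major complication can be dated. Death has a recorded day, and leak, conduit necrosis and chylothorax have diagnosis days. Coverage is partial, not absent.

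**Conclusion.** The point holds as an omission with a practical consequence. Nothing in the plan prevents marker values taken after leak diagnosis from entering variable selection and both models, so the reported performance may not be that of early warning. Confidence in the omission is high; the size and sign of the effect are unknown.

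Under the stated assumptions (mean 7, SD 3 to 5, 16% leaks, 847 patients, all measured), roughly a third to a half of leaks could contribute post-diagnosis day-6 values, and far fewer would for day 4. The concern therefore falls mainly on day 6. The shares depend on an assumed spread and on one oesophageal series, and should not be read as limits. The counts scale with the number of patients and the leak rate, and section 4 allows that "the final sample size may be smaller depending on the proportion of complications detected".

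This should be settled before analysis, because it decides what question the main objective answers.

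**What to change.** In the data analysis section, fix the prediction day or days before analysis; the choice is the sponsor's. For each day:
- include only patients alive with no leak diagnosed;
- use only values available by that day, and drop candidates not yet known, such as pathological stage if unreported;
- predict leaks diagnosed afterwards within a stated horizon, noting that follow-up is 90 days;
- state how leaks diagnosed on the prediction day itself are handled, since only the day is recorded, and report the other rule as a sensitivity analysis;
- report performance for that day.

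The leak model needs no new field, patients or tests, because the diagnosis day is already collected. The real cost is events: about 85-110 leaks after day 4 and 57-69 after day 6, under the assumptions above. Fewer predictors can then be supported. Preoperative plus days 1 to 4 already gives 5 × 20 = 100 marker values. The accuracy figure may also be less favourable.

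Apply the same rule to the secondary major-complication model. The single Clavien-Dindo grade carries no date, and the recorded diagnosis and mortality days date only some of these events. Full coverage would need one added field, the date of the first major complication.

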Peritoneal levels of IL-6 and TNF $\alpha$  were significantly higher in patients with colorectal anastomosis leak compared to patients without leak in some studies and may contribute to their early detection (18), having found that increased levels Serum IL-6 is a predictor of AF in gastrointestinal surgery (24).

In the retrospective study of 330 patients carried out by Yansen et al (25), the neutrophil-lymphocyte ratio (NLR) was used as a biochemical marker. The incidence of AF was 16%, 47.2% of them being treated by surgery. An increasing trend in RLN was significantly associated with the need for surgical intervention, with the mean leak diagnosis time being 7 days and 49.1% being grade III AF. An NLR cut-off value of 10 at the 3rd POD had 74.5% sensitivity, 58% specificity, 25% positive predictive value, and a value of less than 10 had 92.4% negative predictive value for leaks. The results of this study concluded that the value of NLR is more relevant in its negative predictive values and helps in making postoperative decisions with more confidence. On the contrary, an increasing trend of RLN between 1st and 3rd DPO is an independent factor of AF that should be alerted to its suspicion.

Findlay et al (26) developed a prospective study of 326 patients where it was concluded that the use of elevated inflammatory markers is more useful in diagnosis than in prediction, therefore, these parameters do not seem to be very useful for diagnosis and management. early AF. Similar conclusions were obtained in the work published by Liesenfeld et al (20) where the CRP, RGB and NU scores are not recommended as independent markers for the prediction of AF after transthoracic esophageal resection. Another retrospective study by Sugimoto et al (13) of 295 patients analyzed preparatory inflammatory and nutritional markers and studied their relationship with the appearance of postoperative AF in esophageal cancer. The study compared the predictive capacity of preoperative CAR, nutritional prognostic index (PNI), and mGPS for AF, and identified that an elevated value of preoperative CAR ( $\geq 0.0139$ ), but not PNI or mGPS, is a useful indicator for predict the occurrence of AF after esophagectomy. The results of their study suggest that preoperative CAR is a promising predictive marker of AF.

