## **6.- Intervention**

The patient will undergo the indicated surgical intervention depending on whether it is an esophageal or gastric neoplasm, with curative intent with or without prior neoadjuvant treatment. Surgical intervention and postoperative care will be carried out in each of the centers of the national territory that commit to participate according to their usual clinical practice. Thus, the perioperative management and care protocol will be that of each center without the need to apply exceptional measures (beyond the control of the clinical and analytical variables of this study) or a homogeneous protocol in all the participating centers.

The analysis and control of the preoperative clinical variables must be carried out the day before or the same day of the surgical intervention prior to it.

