### **8.2.2.- PREOP (PRE-OPERATIVE) and POST-OPERATIVE DAYS (DAY 1, DAY 2, DAY 3, DAY 4 AND DAY 6)**

These boxes include the variables collected PREOPERATIVELY and during the established postoperative days. These variables are:

- HR (HEART RATE): continuous variable expressed in beats per minute.
- RR (RESPIRATORY RATE): continuous variable expressed in breaths per minute.
- Ta (TEMPERATURE): continuous variable expressed in OC.
- VAS (VISUAL ANALOGUE SCALE): Scale used to assess the degree of pain. Ordinal variable from 1 to 10.
- TAS (SYSTOLIC ARTERIAL PRESSURE): continuous variable expressed in mmHg.
- DBP (DIASTOLIC ARTERIAL PRESSURE): continuous variable expressed in mmHg.
- SAT O2 (OXIGEN SATURATION): continuous variable expressed in %.
- DIURESIS (DIARIES VOLUME OF DIURESIS): continuous variable expressed in ml/day.
- LEUKES (LEUKOCYTES): continuous variable expressed in number/ $\mu$ L.
- LYMPHOS (LYMPHOCYTES): continuous variable expressed in number/ $\mu$ L.
- NEUTRAL (NEUTROPHILS): continuous variable expressed in number/ $\mu$ L
- HB (HEMOGLOBIN): continuous variable expressed in g/dL.
- PLATELET (PLATELET): continuous variable expressed in number/ $\mu$ L
- CREATININE (CREATININE): continuous variable expressed in mg/dL.
- PROTEINS (PROTEINS): continuous variable expressed in g/dL.
- ALBUMIN (ALBUMIN): continuous variable expressed in g/dL.
- CRP (C-REACTIVE PROTEIN): continuous variable expressed in mg/L.
- PROCAL (PROCALCITONIN): continuous variable expressed in ng/mL.
- IL 6 (INTERLEUKIN 6): continuous variable expressed in pg/ml.
- QUICK (QUICK INDEX): continuous variable expressed in %.

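### The one-at-a-time p<0.1 screen can drop preoperative values that help only alongside their postoperative values, and the logistic model has no rule to keep them

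*Combined protocol and SAP*

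**What the plan says.** Section 8.2.2 (Material and methods) lists 20 markers by count, 8 clinical and 12 laboratory, and says "These boxes include the variables collected PREOPERATIVELY and during the established postoperative days". Section 6 (Intervention) sets the timing of the preoperative clinical measurements: "The analysis and control of the preoperative clinical variables must be carried out the day before" or on the day of surgery, ahead of the operation.

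Under Data collection and analysis, section 2 (Data análisis), the sequence is as follows.

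- "A univariate study will be performed to relate the variables studied with the appearance of AF and major postoperative complications", using chi-square or Fisher, t or Mann-Whitney tests.
- Variables with p<0.1 after application "of the corresponding tests will be considered as related or candidates to predict AF or major" complications. The plan explains the loose threshold as a way to avoid losing potentially influential variables.
- Logistic regression follows, with a check that every variance inflation factor (VIF) is below 2.
- Separately, a multilayer perceptron (ANN) is developed. Its inputs are not listed.

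The section names no change from the preoperative value, no trend variable, and no preoperative covariate protected from screening.

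**The concern.** A preoperative measurement can contribute in two ways. It may predict leak by itself, or it may separate a patient's usual level from the change after surgery. A creatinine or platelet count on day 3 mixes both components, and knowing the preoperative value removes the first. That contribution exists only jointly with the postoperative value, so a univariate test of the preoperative value has no power to detect it. A threshold chosen so as not to lose useful variables will usually lose this kind.

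The plan's own rationale refers to movement within a patient. The Introduction cites a falling CRP as reassuring and a rising neutrophil-lymphocyte ratio as an independent factor for leak. None of this reaches the model specification. At stake is the discrimination of a model intended for a web or mobile tool used in postoperative decisions. The data needed to avoid the loss will already have been collected.

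**Working it through.** **Inputs from the documents.** N = 847; 20 markers measured before and after surgery; p<0.1 screen; VIF<2. The sample-size section gives no rate for leak alone. The 30% is for major complications including leak, and one cited series had 16% ("The incidence of AF was 16%, 47.2% of them being treated by surgery"). Leak rates of 10%, 16% and 30% are used as a range.

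**Assumed, because the documents give no values.** Correlation r between the pre- and postoperative values; standardised difference between leak and no-leak patients in the postoperative value (d) and in the preoperative value (d0, same direction).

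**1. The plan's N.** n = z²p(1−p)/precision² = 1.96² × 0.30 × 0.70 / 0.03² = 896.3, so 897. The plan states 847, which corresponds to a precision of 1.96 × √(0.21/847) = 3.09 points. This mismatch is a separate matter and does not affect what follows; 847 is used as stated.

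**2. Chance that a preoperative value passes p<0.1.** With δ = d0 × √(n1·n0/N), P = Φ(δ − 1.645) + Φ(−δ − 1.645). Example at 16% leaks: n1 = 136, n0 = 711, √(136 × 711/847) = 10.68. For d0 = 0.2, δ = 2.14 and P = 0.69.

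| d0 | 10% leaks | 16% | 30% |
|---|---|---|---|
| 0 | 10% | 10% | 10% |
| 0.1 | 23% | 29% | 38% |
| 0.2 | 54% | 69% | 85% |
| 0.3 | 84% | 94% | 99% |

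A null preoperative value is dropped 90% of the time at any sample size. From d0 = 0.2 most are kept.

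**3. AUC for one marker, closed form.** Postoperative value alone: Φ(d/√2). With the preoperative value: Φ(D/√2), where D² = (d² − 2r·d·d0 + d0²)/(1 − r²). For d = 0.5 and d0 = 0 the AUC is 0.638 alone, and 0.641, 0.658 and 0.690 with the preoperative value at r = 0.2, 0.5 and 0.7. For d = 0.8 it is 0.714 alone, and 0.718, 0.743 and 0.786.

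**4. The same by simulation.** N = 847, 16% leaks, 150 runs per setting, AUC on 20,000 new patients. The postoperative value is always in the model and the VIF check is not applied. Each cell gives AUC with the preoperative value screened, then with it always kept.

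| d, d0 | r=0.2 | r=0.5 | r=0.7 | r=0.8 |
|---|---|---|---|---|
| 0.5, 0 | 0.638 / 0.639 | 0.640 / 0.657 | 0.642 / 0.688 | 0.647 / 0.720 |
| 0.8, 0 | 0.715 / 0.717 | 0.716 / 0.743 | 0.720 / 0.785 | 0.726 / 0.826 |
| 0.5, 0.2 | 0.639 / 0.639 | 0.638 / 0.638 | 0.645 / 0.647 | 0.654 / 0.662 |
| 0.8, 0.2 | 0.714 / 0.713 | 0.718 / 0.721 | 0.738 / 0.747 | 0.759 / 0.778 |

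**5. VIF.** For a pair alone, VIF = 1/(1 − r²), which reaches 2 at r = 0.707. It is 1.96 at r = 0.7 and 2.78 at r = 0.8. The plan does not say what is done on a breach. If a variable is removed, the pair is split exactly where keeping it helps most.

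**6. More than one day and more than one marker.** With two postoperative days in the model (d 0.3 to 0.5, correlation between days 0.7 to 0.8) and a null preoperative value, the closed form still gives a gain of 0.016 to 0.027 at r = 0.5 and 0.045 to 0.073 at r = 0.7. In a simulation with 20 markers (500 to 847 patients, 12% to 16% leaks, assumed effects), keeping the preoperative value of each retained marker gained about 0.01 to 0.07 when those values were null and r was at least 0.4. When they were modestly associated with leak, the result was about −0.006 to +0.02. Forcing in all 20 preoperative values could lose up to 0.018.

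**7. Change score.** With d0 = 0 and equal variances, the AUC is Φ(d/(2√(1 − r))). For d = 0.5 this is 0.610 at r = 0.2, below the raw value; 0.638 at r = 0.5, equal to it; and 0.676 at r = 0.7, below the 0.690 from entering both.

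**The case against.** Several points on the other side are sound.

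- **Silence is not a rule.** A reader might infer that markers enter only as raw postoperative levels. The plan never says so. Section 4.1.4 under Stages of development foresees calculated variables without naming them, and change or trend terms may be among them.
- **The neural network.** A reader might infer that the screen strips preoperative values from every model. The text ties p<0.1 to candidate status, with logistic regression next, and introduces the network separately. A perceptron given both values could learn the adjustment.
- **Preoperative values may predict leak themselves.** The Introduction argues that malnutrition, low protein and inflammation impair healing, and a cited retrospective study of 295 patients found the preoperative CRP-albumin ratio predictive. Such values tend to pass, and forcing them in then adds little (step 4, lower rows).
- **Which markers benefit.** The documents give no leak effect for the markers most likely to have stable levels, such as creatinine, haemoglobin or blood pressure. Some of the cited evidence uses raw cut-offs on a given postoperative day. Where the preoperative level says little about the postoperative one, as is plausible for CRP, the gain is small.
- **Earlier postoperative days** may serve as the patient's own reference. Step 6 suggests this is only partial, on assumed inputs.

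These points limit the reach and size of the problem. They do not supply a pre-specified use of the preoperative values in the logistic model. The secondary objectives that use preoperative scores or describe the evolution of markers do not do so either.

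**Conclusion.** The point holds for the logistic route. Read naturally, the screen decides what enters the model. It drops a preoperative value with no leak association of its own about 90% of the time, and the VIF check can split a pair with |r| above 0.707.

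For one marker with a null preoperative value, the AUC loss is negligible at r about 0.2, roughly 0.02 to 0.03 at r = 0.5, and about 0.05 or more at r = 0.7. For a modestly predictive preoperative value (d0 about 0.2) it is close to nil unless r is about 0.7 or higher, and at most about 0.02 in the settings run. All of this rests on assumed correlations, effect sizes and leak rates. The loss in the plan's actual model, with many markers over five postoperative days, cannot be computed from the documents.

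The stronger conclusion that most of the 20 preoperative values are discarded and accuracy is necessarily lost is not supported. It would need nearly all of them to be close to null (d0 about 0.1 or less) and the same screen to govern the network. The documents establish neither.

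**What to change.** Add to the data analysis section:

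- Each postoperative marker retained for the logistic model is entered together with its own preoperative value as a covariate, on the log scale for skewed markers such as CRP, procalcitonin and IL-6.
- That covariate is exempt from the p<0.1 screen and from removal on VIF grounds.
- The neural network receives the preoperative values among its inputs.

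Do not offer a simple change score as an equivalent: below r = 0.5 it does worse than the raw postoperative value (step 7). Do not force in preoperative values of markers that are not retained, since that can cost accuracy (step 6).

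The cost is wording only, because the data are already to be collected. The price in the model is one extra parameter per retained marker. When the pre/post correlation is low, there may be a very small AUC loss, under about 0.01.
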